14.3 Quality Assurance Audits and Regulatory Agency Inspections

The study site may be research subject to audits by the sponsor or its designee. In such a case, the auditor designated by the sponsor shall contact the study site in advance to determine the date of audit. The auditor may ask to visit the facilities where laboratory specimens are collected and any other facilities used during the clinical research. In addition, this research may be inspected by regulatory agencies, including those of foreign governments (e.g., the Food and Drug Administration [FDA], the United

Kingdom Medicines and Healthcare products Regulatory Agency [MHRA]). If the study site is contacted for an inspection by a regulatory body, the sponsor should be notified promptly. The principal investigator and the chief executive of the study site shall ensure that the auditor has access to all the research-related source documents.

15.0 ETHICAL CONDUCT OF CLINICAL RESEARCH

This research shall be conducted with the highest respect for the individual participants (i.e., research subjects) according to the research protocol, and the ethical principles that have their origin in the Declaration of Helsinki, Ethical Guidelines for Medical and Health Research Involving Human Subjects. Each investigator will conduct the study according to regulatory requirements and in accordance with "Responsibilities of the Investigator" in Appendix B.

15.1 Approval of the Ethical Review Board, etc.

The Ethical Review Board, etc., shall be constituted in accordance with the regulations For implementation or continuation of this study, the principal investigator will provide the head of the medical institution with this protocol, a copy of the informed consent form and other documents required by applicable regulations. The head of the medical institution will then request a review to be done by the institutional review board etc. regarding essential items for proper implementation of the clinical study, including whether the protocol is compliant with the Ethical Guidelines for Medical and Health Researches Involving Human Participants. Documentation of approval of the institutional review board etc. and agreement of the head of the medical institution must be obtained by the principal investigator before implementation or continuation of the study.

The study site shall observe all requirements that the Ethical Review Board, etc. prescribe. The requirements may include notifications to committees such as the IEC, for example, revision of the research protocol, revision of the informed consent form and information sheet, reports on safety in accordance with the regulatory requirements, reports on status of implementation of the research at intervals determined by a study site committee such as the Ethics Review Committee, and submission of the study completion report.

15.2 Conflict of Interests

Prior to the conduction of this clinical research, the investigators involved in this clinical research shall ensure appropriate management of any conflicts (COI) in the conduct of the research in accordance with the rules of the study site.¹⁵⁾⁻¹⁹⁾

The study site shall comply with all requirements specified by a committee such as the Ethics Review Committee, including the COI self-statement form, the research protocol, and the informed consent form and information sheet.

15.3 Informed Consent and Information Sheet, and the Agreement of the Research Subjects

The informed consent and information sheet form shall contain specific requirements of the Declaration of Helsinki, Ethical Guidelines for Medical and Health Research Involving Human Subjects and all applicable laws and regulations. The informed consent form and information sheet shall specify the use of personal information and medical information of research subjects in this clinical research (both in and outside Japan: supply to a third party), and disclosure. The informed consent form and the information sheet will explain in detail the nature of the research, its objectives, and potential risks and benefits. The informed consent form will detail the requirements of the participant and the fact that research subject is free to withdraw at any time without giving a reason and without any negative effect on the further medical care.

The principal investigator is responsible for the preparation, contents, and approval of the informed consent form and research subject information sheet by the committee such as the IEC. The informed consent form and information sheet must be approved by the committee prior to use.

The informed consent form and information sheet shall be written in language that can be easily understood by the potential research subjects. The principal investigator or investigator shall be responsible for providing detailed explanation of the informed consent form and information sheet to the potential subjects. Information should be given in both oral and written form whenever possible and in manner deemed appropriate by the committee such as the IEC.

The principal investigator or investigator shall ensure that the potential research subjects (or the representatives) have (1) an opportunity to inquire about the research and (2) sufficient time to decide on their participation. If a potential research subject (or their representative) decides he or she is willing to participate in the research, then the informed consent form must be signed and dated by the potential research subject (or the representative) prior to entering into the research as a subject. The principal investigator or investigator shall instruct the potential research subject (or representative) to sign using their legal names, not nicknames, using a blue or black ball point ink pen. Also the principal investigator or investigator shall sign and date the informed consent form prior to entering into the research.

Once signed, the original informed consent form shall be retained by the principal investigator or investigator. The principal investigator or investigator shall record the date that the potential research subject signed the informed consent form in the subject's

medical record. A copy of the signed informed consent form shall be given to the research subject.

The principal investigator or investigator shall follow the same procedure as for obtaining the initial consent when newly obtaining re-consent from the concerned research subject (or the representative) when the informed consent form is revised. The date of obtaining new consent shall be recorded in the research subject's medical record, and a copy of the revised consent form shall be provided to the research subject.

15.4 Personal Information of the Research Subjects

The sponsor or the designee shall affirm the principle of the protection of research subjects' private/personal information. Throughout this study, research subject ID numbers shall be used to link the subject's source data to the sponsor's research database and research-related documents. Limited information on research subjects such as gender, age, and date of birth may be used within the scope of all applicable laws and regulations for identification of research subjects and confirmation of accuracy of research subject ID number.

For verification of the conduct of the research in compliance with this protocol and the Ethical Guidelines for Medical and Health Research Involving Human Subjects, the sponsor shall require the principal investigator to provide the research sponsor's designee, representatives of regulatory authorities, designated auditors, and committees such as the Ethical Review Board direct access to research subjects' original medical records (source data or documents), including laboratory test results, ECG results, admission and discharge records during a subject's research participation, and autopsy reports.

The principal investigator or investigator shall obtain specific authorization of the research subject as part of the informed consent process for access to research subject's original medical records by research sponsor's designee and representatives of regulatory authorities (see Section 15.3).

When providing a copy of source documents to the sponsor, the principal investigator or investigator shall delete information that may lead to identification of an individual (name and address of research subject, other personal information not recorded on the CRF of the research subject).

15.5 Consultation Windows for the Research Subjects or Persons Related to the Research Concerned

The principal investigator shall establish a contact service to respond to inquiries concerning this clinical research from research subjects or concerned people. Details of the contacts for inquiries will be described in the ICF.

15.6 Financial Burden or Reward to the Research Subjects

Of the expenses for this clinical research, the sponsor shall offer compensation for medical treatment not covered by health insurance as research expenses.

The research subjects shall pay expenses for medical treatment covered by ordinary health insurance.

In addition, the principal investigator shall pay expenses such as transportation expenses for participation in this clinical research to the research subjects at each visit from the research funds. Details of the financial burden on the research subjects and rewards shall be described in the informed consent form and information sheet.

15.7 Benefits and Inconveniences to the Research Subjects

15.7.1 Benefits to research subjects

Participation in this study is expected to allow more detailed characterization of the pathological condition of insomnia based on objective measurements, leading to selection of more appropriate treatment in individual patients.

15.7.2 Inconveniences to research subjects

Certain insomnia medications will be restricted during participation in this study.

15.8 Attribution of Research Results and Access Rights

15.8.1 Attribution of research results

The research results and data obtained from this research shall belong to the sponsor. In addition, secondary use (metaanalysis, etc.) of the data obtained in this clinical research may be possible if used in such a way that the data shall not be linked to personal identification information.

15.8.2 Data access rights

Access rights for all data and information generated from this study will be given to personnel approved by the sponsor.

15.9 Reporting of Results, Publication, Disclosure, and Clinical Research Registration Policy

15.9.1 Reporting of results, publication and disclosure

The principal investigator shall report a written summary of results of the research to the chief executive of the study site and provide the sponsor with all the results and data obtained from the research. Only the sponsor may disclose the research information to other principal investigators, investigators or regulatory authorities during the research period, except when required by laws and regulations. The sponsor shall be responsible for publication of the research protocol and research-related results (including the public web site) except for other cases permitted in the research contract.

During research period and after the end of research, the sponsor or its designee should promptly summarize the results and present it to medical journals and academic conferences, etc. The sponsor may publish any data or information obtained from the research (including data and information provided by the principal investigator) without obtaining agreement of the principal investigator.

The investigator or the subinvestigator should obtain the prior written approval from the sponsor when publishing the information obtained in this research at an academic conference, etc.

15.9.2 Clinical research registration

To ensure that information on clinical research is made accessible to the public in a timely manner and to comply with applicable laws, regulations, and guidelines, Takeda Pharmaceutical Company Limited shall register all clinical research being conducted in patients around the world at public trial registration sites, including at least the website(s) of ClinicalTrials.gov and Japan Pharmaceutical Information Center Clinical Trials Information (JAPIC), before initiation of the clinical research. On such websites, the research location (city, country), subject recruitment status, and contact information for Takeda Pharmaceutical Company Limited are open to the public.

15.9.3 Clinical trial results disclosure

Takeda Pharmaceutical Company Limited shall post the research results, irrespective of the nature of the results, at the public trial registration sites of ClinicalTrials.gov and JAPIC in accordance with applicable laws and regulations.

15.10 Insurance and compensation for injury

The research subjects participating in this research shall be compensated for any injury resulting from participation in the research according to local regulations applicable to the study site. The sponsor or its designee shall buy an insurance policy to compensate for health injury in research subjects

10.2. Handling of Dropouts or Missing Data.....	18
10.3. Criteria for Interim Analysis and Early Discontinuation	18
10.4. Multicenter Studies	18
10.5. Multiple Comparisons/Multiplicity.....	18
10.6. Examination of Subgroups.....	18
11. REVISION HISTORY	19

1. DEFINITIONS of TERMS

- TEAE: Treatment-emergent adverse event
- Summary Statistics: Number of subjects, mean, standard deviations (SDs), maximum values, minimum values and quartiles
- Treatment Group: Ramelteon group

2. TIME WINDOW

[Actigraphy, Sleep diary]

Since the response data of actigraphy and sleep diary at each time point are the mean of data which collected in the previous 7 days, a set of data before each time point will be evaluated if they meet in the time window. For example, if a set of data belongs to the both time windows at week 4 and week 8, a set of data will be divided into two groups, which are for Week 4 and Week 8.

When there are two or more sets of data in the same time window, the one with the nearest visit date to the reference date will be selected, and if the time differences from the reference date are the same, the later data will be adopted.

Assessment time point	Reference Date	Time window
		Days after the first administration
At the start of the treatment period (baseline)	Day 1	Day -7 to Day 1
Week 4 of the treatment period	Day 29	Day 2 to Day 32
Week 8 of the treatment period	Day 57	Day 33 to Day 60
At the end of the treatment period	The latest set of the data group during the treatment period	Day 2 to Day 60

The day before the first day of the administration will be referred to as Day -1, and the first day of administration as Day 1.

[PGI, HAM-D17, 3DSS, Weight]

When there are two or more data in the same time window, the one with the nearest assessment date to the reference date will be selected, and if the time differences from the reference date are the same, the later data will be adopted.

Assessment time point	Reference Date	Time window
		Days after the first administration
At the start of the treatment period (baseline)	Day 1	Day -7 to Day 1
Week 4 of the treatment period	Day 29	Day 2 to Day 32
Week 8 of the treatment period	Day 57	Day 33 to Day 60
At the end of the treatment period	The latest day during the treatment period	Day 2 to Day 60

The day before the first day of the administration will be referred to as Day -1, and the first day of administration as Day 1.

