5.2 Endpoints

5.2.1 Primary endpoint

Change in actigraphy-measured sleep latency* from baseline (i.e., start of the study treatment period) to the end of the treatment period

*: Mean value from the past 7 days

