9.1.7 Actigraphy

At the end of the informed consent, an actigraph will be lent to each participant. After full instructions on actigraphy are provided to the participants, actigraphy recording will be started. Patients meeting the inclusion criteria on the basis of the data in the run-in period will keep the actigraph, and be instructed to wear it until the end of the treatment period.

Participants will be instructed to bring the actigraph at each study visit. For analysis of the data recorded in the actigraph, the actigraph will be connected to a computer with an actigraphy data analysis software installed, and the following data will be transferred to the analysis software: sleep latency, total nocturnal sleep time, nocturnal wake time, the number of nocturnal awakenings, sleep efficiency and daytime activity level (step counts). For each of these parameters, the validity of the measured data will be checked according to the "Procedures for actigraphic sleep assessment" prepared separately, and the data during the run-in period (Weeks -1 to 0) and the treatment period (Weeks 3 to 4 and 7 to 8) will be recorded in the case report form. The actigraph device will be retrieved after completion of the actigraphy recording on the 3 occasions, or when the participant is withdrawn from the study.

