7.3. Other Analyses

7.3.1. Patient Global Impression of Improvement (PGI)

Analysis set: Full Analysis Set

Analysis items: PGI [Very much worse, Much worse, A little worse, No change, A little improved, Much improved, Very much improved]

Time Point: End of the treatment period

Analysis Methods: For the above analysis items, the following analysis will be performed

- (1) The number of subjects and the percentage will be calculated for each category.

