10.2. Handling of Dropouts or Missing Data

Any imputation for missing data will not be performed.

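### SAP 2 windows label Days 33-42 as Week 8, divide 7-night sets at Day 32/33 with an ambiguous end-of-treatment value, and leave a PGI after Day 60 out of its only analysis

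*SAP*

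**What the plan says.** SAP 2 has two window tables with the same limits, one for actigraphy and sleep diary and one for PGI, HAM-D17, 3DSS and weight. Week 4 has reference Day 29 and runs from Day 2 to Day 32. Week 8 has reference Day 57 and covers "Day 33 to Day 60". End of treatment accepts Day 2 to Day 60.

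Three further rules apply to actigraphy and diary:
- If a set belongs to both the Week 4 and Week 8 windows, "a set of data will be divided into two groups, which are for Week 4 and Week 8".
- If a window holds more than one set, "the one with the nearest visit date to the reference date will be selected".
- The end-of-treatment value is "The latest set of the data group during the treatment period".

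Protocol 5.2.1 defines the value behind the primary endpoint as "Mean value from the past 7 days". Protocol 9.1.7 states that data from the run-in and from "the treatment period (Weeks 3 to 4 and 7 to 8) will be recorded in the case report form". Validity is checked under a separate actigraphy procedure.

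PGI is scheduled only at Visit 4 or withdrawal (Protocol 9.3.3 and 9.3.4). SAP 7.3.1 analyses it at one point only: "Time Point: End of the treatment period". SAP 10.2 adds: "Any imputation for missing data will not be performed".

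**The concern.** Within a window the SAP prefers the value nearest the reference date, but the boundary between Week 4 and Week 8 does not follow that principle. A visit only four days after Day 29 is reported as Week 8. That label matters, because Protocol 6.2 chose 8 weeks on the ground that the effect on sleep latency was greatest around then. The 3DSS asks about the past month, so a Day 33 answer labelled Week 8 describes roughly Days 3-33.

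The rule for dividing a set implies placement night by night, whereas the rule for choosing between sets works by visit date. The end-of-treatment row does not say whether a divided set counts whole or in part. Two programmers following the text could therefore derive different primary values for the same withdrawn patient. A one-night fragment would also make the daily variation in SAP 5 (maximum minus minimum latency) zero by construction.

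A final visit after Day 60 is in no window. Its PGI drops out of the only PGI analysis, and end of treatment for HAM-D17, 3DSS and weight falls back to the earlier visit.

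**Working it through.** **Inputs.** Windows and reference days are from SAP 2, the 7-day mean from Protocol 5.2.1, and the 30 planned patients from Protocol 13.3. Assumption: a set is nights V-7 to V-1 for a visit on Day V.

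**1. Reference days reproduced.** Day = 1 + 7 × weeks: 1 + 28 = 29 and 1 + 56 = 57. Both agree with the SAP.

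**2. Window offsets.** Week 4: 2 - 29 = -27 and 32 - 29 = +3. Week 8: 33 - 57 = -24 and 60 - 57 = +3.

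**3. Days nearer Week 4 but labelled Week 8.** The midpoint is (29 + 57)/2 = 43. Day 33 is 4 days from Day 29 and 24 from Day 57. Day 42 is 13 and 15 days away. Day 43 is 14 from each. So Days 33-42 are all nearer Day 29, and Day 43 is a tie.

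**4. Divided sets.** Nights up to Day 32 number 40 - V, and nights from Day 33 number V - 33.

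| Visit day V | Week 4 nights | Week 8 nights |
|---|---|---|
| 34 | 6 | 1 |
| 35 | 5 | 2 |
| 36 | 4 | 3 |
| 37 | 3 | 4 |
| 38 | 2 | 5 |
| 39 | 1 | 6 |

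In every row all 7 nights also lie in Day 2-60. A patient who withdraws on Day 36 thus has a primary value from 7 nights or from 3, depending on the reading. If the visit day itself is counted, the affected visits are Days 33-38.

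**5. Fixed-week reading.** If the case report form holds fixed Weeks 3-4 and 7-8 (about Days 22-28 and 50-56), all 7 nights of each set fall in their own window and no scheduled set is divided.

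**6. Precision for one patient.** With independent nights and 7 baseline nights (both assumptions), the night-to-night error of the change from k end nights, relative to a full set, is √[(1/7 + 1/k)/(2/7)]. This gives 2.00 for k = 1, 1.29 for k = 3 and 1.04 for k = 6.

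**7. Precision of the trial mean.** Suppose one of 30 patients has a fragment and, as an extreme, all variance in the change is night-to-night. The standard error is multiplied by √[(29 + r²)/30], where r is the ratio in step 6.
- k = 1: √(33/30) = 1.049, an increase of 4.9%.
- k = 3: √(30.67/30) = 1.011, an increase of 1.1%.

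Between-patient variance makes both smaller.

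**8. Late Visit 4.** A PGI on Day 61 or later is in no window. Each one is 1/30 = 3.3% of the planned sample. For actigraphy and diary placed night by night, 68 - V nights remain: 7 at Day 61, 6 down to 1 at Days 62-67, and 0 at Day 68. Placed by visit date, none remain from Day 61. Under the fixed-week reading with night-by-night placement, none are lost.

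**The case against.** The strongest reply concerns the primary endpoint. A reader might infer that SAP 2 makes a fragment of 1-6 nights the primary value. The text does not compel that. The division is written for Week 4 and Week 8, end of treatment has its own row, the whole set lies inside that row, and the same section describes each response as a mean over the previous 7 days. This reply stands, and what remains is an ambiguity.

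A reader might also infer that the Week 4/Week 8 boundary shifts the primary result. As long as sets are kept whole it does not, because end of treatment takes the latest set in Day 2-60 wherever the boundary lies. Likewise, a Day 33-42 value serves as Week 8 only when no final visit falls in Day 33-60.

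Nor is a late PGI thrown away, since SAP 9 lists it. A cap that keeps end of treatment close to dosing is defensible when treatment lasts 8 weeks. However, the exposure categories in SAP 6.3.2 include 58 days or more, so the SAP itself allows for longer dosing.

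Finally, the reach is narrow. Division needs a visit on one of six days and disappears under the fixed-week reading. Visit tolerances (Protocol Appendix A) and any minimum number of nights in the actigraphy procedure are not in the supplied documents. The study is exploratory and its sample size has no power basis. All of this limits the severity. It does not restore an empty Week 4, settle the ambiguous value or bring a late PGI into its analysis.

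**Conclusion.** The point holds as a minor one. Three consequences follow from the stated windows: Days 33-42 carry the Week 8 label although nearer Day 29; a Visit 3 in that range leaves Week 4 empty for HAM-D17, 3DSS and weight; and a PGI after Day 60 is omitted from its only summary. Division of sets for visits on Days 34-39 rests on the assumption that a set is the 7 nights before the visit. Under that assumption the Week 4 and Week 8 fragments depart from the 7-day definition, and the end-of-treatment value of a last, divided set is not uniquely determined.

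How many patients this touches cannot be worked out from the documents. With one affected patient in 30, the standard error of the primary mean rises by at most about 5% under assumptions chosen to exaggerate the effect, so the influence on the primary mean is likely small.

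**What to change.** In SAP 2:
1. In both tables, put the Week 4/Week 8 boundary at the midpoint and state which side Day 43 belongs to.
2. Delete the division rule. Assign each 7-night set whole to one time point by its visit date, and state that the end-of-treatment set is never divided. Moving the boundary alone would only move the problem: with Week 4 ending on Day 43, visits on Days 45-50 would be divided instead.
3. State whether a set is the 7 nights before the visit or fixed study weeks. Apply a minimum number of valid nights consistent with the actigraphy procedure.
4. Replace the Day 60 cap with one stated limit tied to the last dose and applied alike to all endpoints, so that a late Visit 4 or withdrawal assessment within it is analysed. List the study day of any assessment after the last dose.

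The cost is table edits and light reprogramming, with no new data. There are three downsides. A few very short sets leave the analysis. Withdrawals up to about Day 43 no longer supply a Week 8 value, though they still supply end of treatment. Some late values may fall shortly after the last dose. When the limit is chosen, check that it does not drop withdrawal assessments that the present windows accept.
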